4.7 Study Discontinuation

Participants who discontinue study drug(s) but are still on study in the follow-up period can be terminated from the study for the following reasons:

- Completed protocol-defined follow-up period
- Death
- Lost to follow-up
- Investigator decision
- Study terminated
- Participant withdrew consent from study

4.8 Study Duration

For individual participants, the study duration is approximately 14 weeks in Part 1A and Part 1B. The study duration is approximately 19 weeks in Part 2. The study duration includes screening, dosing, follow-up, and an end of study visit.

The overall study duration is approximately 24 months. This estimate may vary from that observed in the actual conduct of the study.

4.9 End of Study

The end of study for each participant occurs when study discontinuation criteria are met per **Section 4.7**.

The end of the overall study occurs at the time of study database lock. Database lock occurs when the last participant has met off-study criteria and the data collection process is complete.

5 ELIGIBILITY CRITERIA

All inclusion criteria and no exclusion criteria must be met to enroll. No exceptions to these criteria will be granted by the sponsor.

5.1 Inclusion Criteria

1. Ability to provide informed consent. Participants must be willing and able to comply with study procedures.
2. Aged ≥ 18 years and ≤ 70 years of age.
3. HIV-1 infection documented by rapid HIV test or HIV enzyme or chemiluminescence immunoassay (E/CIA) test and confirmed by Western blot or a second antibody test (other than the initial rapid HIV test or E/CIA), HIV-1 antigen, or plasma HIV-1 RNA viral assay.
4. Plasma HIV-1 RNA viral load must meet the following conditions:
 - a. < 50 copies/mL at 2 time points within 24 months prior to screening (1 time point within 12 months prior to screening).
 - b. < 50 copies/mL at screening.
 - c. Not ≥ 50 copies/mL on 2 consecutive time points within 24 months nor > 1000 copies/mL at any time within 6 months prior to screening.
5. On continuous ART for at least 24 months prior to screening and must continue ART throughout the study. Participant must not have missed > 9 total days or > 4 consecutive days in the 3 months prior to screening. No changes in ART medication or modifications of ART dosing are allowed within 30 days prior to screening. Permitted ART regimens include:
 - a. At least 3 ART drugs (< 200 mg ritonavir [total daily dose] or cobicistat [any dose] are not considered as one of the 3 ART drugs). One of the ART drugs must include an integrase inhibitor, non-nucleoside reverse transcriptase inhibitor (NNRTI), or boosted protease inhibitor.

or

 - b. At least 2 ART drugs, in which one of the drugs is either a boosted protease inhibitor or an integrase inhibitor, that are Food and Drug Administration (FDA) approved or are recommended by Department of Health and Human Services Treatment Guidelines.
6. CD4 cell count > 350 cells/ mm^3 at screening.
7. Hepatitis C virus (HCV) antibody negative or HCV RNA negative.
8. Hepatitis B surface antigen negative.
9. Adequate vascular access.

10. Clinical laboratory parameters obtained at screening as follows:
 - a. Platelet count $\geq 125 \times 10^3/\mu\text{L}$.
 - b. Absolute neutrophil count $\geq 1.5 \times 10^3/\mu\text{L}$.
 - c. Hemoglobin $\geq 12 \text{ g/dL}$ (male) and $\geq 11 \text{ g/dL}$ (females)
 - d. Prothrombin time or international normalized ratio (INR) $\leq 1.1 \times$ upper limit of normal (ULN)
 - e. Serum total bilirubin $< 1.5 \times$ ULN. If total bilirubin is elevated, direct bilirubin $< 2 \times$ ULN. If ART includes atazanavir, direct bilirubin must be $\leq 1.0 \text{ mg/dL}$.
 - f. Aspartate aminotransferase (AST) and alanine aminotransferase (ALT) $\leq 1.5 \times$ ULN
 - g. Alkaline phosphatase (ALP) $\leq 1.5 \times$ ULN
 - h. Estimated glomerular filtration rate (eGFR) $> 60 \text{ mL/min}$ as determined by the Chronic Kidney Disease Epidemiology Collaboration equation.
 - i. Negative serum pregnancy test for individuals of childbearing potential (IOCBP)
11. IOCBP, defined as assignment of female sex at birth, not surgically sterilized (hysterectomy, bilateral salpingectomy, and bilateral oophorectomy), and between menarche and 1-year post menopause, must have a negative serum pregnancy test performed within 72 hours prior to initiation of study drug. IOCBP must agree to abstain from egg donation during the course of the study.
12. IOCBP and male participants with partners of IOCBP must agree to use highly effective methods of contraception according to **Section 8.1.3** from the time of consent through 6 months after discontinuation of study drug. Male participants must agree to abstain from sperm donation during the course of the study.
13. IOCBP is not pregnant, expecting to become pregnant, or breastfeeding or male participant is not expecting to father children within the projected duration of the study, starting with screening visit through 6 months after the last dose of study drug.

5.2 Exclusion Criteria

1. History or other evidence of severe illness, immunodeficiency other than HIV-1, or any other condition, such as known psychiatric or substance abuse disorder, that in the opinion of the investigator would impair the ability to receive, tolerate, or comply with study drug administration or study procedures.
2. History of any HIV-1 vaccine or HIV-1 immunotherapy, except MGD014 or MGD020, within 6 months prior to screening.
3. Clinically significant cardiovascular disease within 12 months prior to screening (unless otherwise stated) including but not limited to:
 - a. Myocardial infarction or unstable angina within the past 6 months.

- b. Cardiac arrhythmias.
- c. Uncontrolled hypertension at screening: systolic blood pressure > 180 mmHg, diastolic blood pressure >100 mmHg that is sustained on repeat measurement (without intervention).
- d. Deep vein thrombosis or pulmonary embolism within the past 6 months.
- e. Cerebrovascular accident within the past 6 months.
- f. QTc prolongation > 480 millisecond calculated from the average of 3 repeat electrocardiograms (ECGs) obtained at screening in approximately 1-minute intervals.
- g. Congestive heart failure (New York Heart Association class III-IV).
- h. Pericarditis.
- i. Pericardial effusion.
- j. Myocarditis.

4. Diabetes mellitus \geq Grade 3 per DAIDS criteria (defined as uncontrolled despite treatment modification or hospitalization for immediate glucose control indicated).
5. Evidence of active viral, bacterial, or systemic fungal infection requiring parenteral antibiotic, antiviral, or antifungal treatment within 7 days prior to the initiation of study drug. Participants requiring any systemic antiviral, antifungal, or antibacterial therapy for active infection must have completed treatment no less than 1 week prior to initiation of study drug.
6. Active coronavirus disease 19 (COVID-19)/severe acute respiratory syndrome coronavirus 2 (SARS-CoV-2) infection. While SARS-CoV-2 testing is not mandatory for study entry, testing should follow local clinical practice guidelines/standards. A positive test result for SARS-CoV-2 infection, known asymptomatic infection, or suspected infection is exclusionary.
7. Active, untreated syphilis (defined as rapid plasma reagin [RPR] positive at screening without history of treatment).
8. Known allergic hypersensitivity to recombinant proteins, | or any excipient contained in the study drug or vehicle formulation for MGD020 or MGD014.
9. History of severe allergic reaction with generalized urticarial, angioedema, or anaphylaxis.
10. History of malignancy that may require systemic anti-cancer therapy or radiation therapy. A history of non-melanoma skin cancer with documentation of complete resection or resolution per licensed and board-certified dermatologist is not exclusionary.
11. History of uncontrolled seizure within the past 2 years. A seizure disorder controlled on anti-epileptic therapy is not exclusionary.

12. History of organ or tissue transplantation.
13. History of autoimmune disease, including type I diabetes mellitus, with the specific exceptions of:
 - a. Vitiligo.
 - b. Resolved childhood atopic dermatitis.
 - c. Psoriasis (except psoriatic arthritis) not requiring systemic treatment (within the past 2 years).
 - d. Euthyroid Graves' disease or non-autoimmune hypothyroidism.
14. History of unstable asthma, including any of the following events within the past 12 months:
 - a. > 1 exacerbation of asthma symptoms treated with oral/parenteral corticosteroids.
 - b. Emergency care, urgent care, hospitalization, or intubation for asthma.
15. History of coagulopathy or other bleeding disorder.
16. Participation in another investigational clinical research study within 60 days prior to screening. The following exceptions apply:
 - a. Enrollment in an ART study using FDA-approved ART.
 - b. Enrollment in the ACTG 5332 REPRIEVE study (NCT02344290) and using FDA-approved pitavastatin provided the participant has been on study for \geq 4 months.
17. Use of any of the following within 90 days prior to planned first dose of study drug: any blood product, immune globulin, immunomodulatory therapy, cytokine therapy, or growth stimulating factors such as systemic corticosteroids, cyclosporine, methotrexate, azathioprine, anti-CD25 antibody, interferon, IL-2, systemic cytotoxic chemotherapy, or investigational therapy. Intent to use immunomodulators (e.g., IL-2, IL-12, interferons, or tumor necrosis factor [TNF] modifiers) during the study.
18. History of virologic failure on an ART regimen containing FDA-approved HIV-1 entry inhibitors (e.g., maraviroc, enfuvirtide, fostemsavir, and/or ibalizumab). Virologic failure is defined as a confirmed plasma HIV-1 RNA \geq 150 copies/mL following assessment of drug adherence, repeat HIV-1 RNA testing with continued treatment, and/or resistance testing.
19. Current use of an FDA-approved HIV-1 entry inhibitor.
20. For participants with prior exposure to MGD020, positive ADA to MGD020.
21. For participants with prior exposure to MGD014, positive ADA to MGD014 (Part 1B or Part 2 only).
22. Prisoners or other individuals who are involuntarily detained.
23. Employees of the sponsor unless approved by the Institutional Review Board (IRB) of record.

24. Any investigative site personnel directly affiliated with this study.

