2.3 Background on Study Drugs

[figure not shown]
The non-clinical studies of MGD020 and MGD014 are summarized in the respective investigator brochures (IBs).

MGD020 (HIV_{7B2} x CD3) and MGD014 (HIV_{A32} x CD3) are fragment crystallizable (Fc)-bearing DART molecules identical in structure except for the sequences of the anti-HIV-1 env arms, which recognize different epitopes of the HIV-1 env. DART molecules are bispecific, antibody-based molecules that can bind two distinct antigens simultaneously. MGD020 and MGD014 are designed to target HIV-1-infected, env-expressing cells for recognition and elimination by CD3-expressing T lymphocytes as effector cells. A schematic depicting the structure and mechanism of action of an HIV-1 x CD3 DART molecule is shown in **Figure 1**.

Prior pre-clinical and clinical studies with MGD014, which is structured exactly like MGD020 except for the identity of the MGD020 anti-HIV-1 env arm, were conducted to evaluate pharmacokinetics (PK) and anti-drug antibodies (ADA). MGD020 and MGD014 are structurally and functionally similar. Therefore, MGD020 will likely have similar PK and ADA in PWH on ART. The first in human dose of MGD020 is based on the minimum anticipated biological effect level (MABEL).

Figure 1

DART Molecule Structure and Mechanism for Redirected T-cell Cytolysis of Human Immunodeficiency Virus-1-infected Envelope-expressing Cells

The anti-CD3 arm (orange) of the HIV-1 x CD3 DART molecule binds to CD3 (brown) at the surface of CD3⁺ T cells (effector cell), and the anti-HIV-1 env arm (dark blue) of the HIV-1 x CD3 DART molecule binds to HIV-1 env antigen at the surface of HIV-1 infected CD4⁺ T cells (target cell). Cell surface HIV-1 env

glycoprotein (light blue) may be in the form of functional mature trimers or nonfunctional variant forms such as cleaved or uncleaved gp160 monomers or gp41 stumps (17); gp160 is the full-length HIV-1 env precursor which is cleaved by furin to generate gp120 and gp41. HIV-1 x CD3 DART molecule-mediated co-engagement of target and effector cells results in activation of CD3+ T-cell cytolytic responses toward HIV-1-infected, env-expressing target cells.

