4.1.2 Part 1B: Single Ascending Dose of MGD020 and Fixed-Dose of MGD014

Part 1B commences only after the MTD or MAD of single-agent MGD020 has been determined in Part 1A. During Part 1B, participants will be enrolled and treated with a single ascending dose of MGD020 in combination with a fixed dose of 300 mcg/kg MGD014.

MGD020 and MGD014 will be administered at the doses shown in **Table 2** using a 3+3 design, beginning with Cohort 1, with at least 72 hours between dosing of each participant within a cohort. The first cohort will be treated with a single dose of MGD020 at a dose determined to be one dose level lower than the MTD/MAD from Part 1A (i.e., one dose level lower than MTD_{1A}/MAD_{1A}). MGD014 is dosed at 300 mcg/kg, as determined from Study CP-MGD014-01.

In Part 1A, the MGD020 dose is increased in half-log increments from 1 to a maximum of 300 mcg/kg. In Part 1B, the maximum starting dose of MGD020 for Cohort 1 of Part 1B will thus be 100 mcg/kg (one dose level below the Cohort 6 dose of 300 mcg/kg). In combination with MGD014 at 300 mcg/kg, this would yield a maximum total DART dose of 400 mcg/kg for Cohort 1 of Part 1B, which is less than a half-log increment over the total DART dose that would have been tolerated in Part 1A.

Escalation to the next cohort follows the rules described in **Section 4.2**.

Table 2 MGD020 and MGD014 Combination Dose Escalation Scheme (Part 1B)

Cohort	MGD020 ^a (mcg/kg)	MGD014 (mcg/kg)	Design
-1 ^b	MGD020 MTD _{1A} /MAD _{1A} -2	300	3+3
1	MGD020 MTD _{1A} /MAD _{1A} -1	300	3+3
2	MGD020 MTD _{1A} /MAD _{1A}	300	3+3

- a Dosing for Part 1B will begin with Cohort 1. The MGD020 dose in Cohort 1 will be one dose level below the single-agent MTD/MAD in Part 1A. For example, if the MTD/MAD in Part 1A for MGD020 is 300 mcg/kg, Cohort 1 of Part 1B would receive 100 mcg/kg MGD020 + 300 mcg/kg MGD014.
- b If the dose level in Part 1B Cohort 1 exceeds the MTD, de-escalation to Cohort -1 may be considered. For example, if MTD is exceeded when the Part 1B Cohort 1 dose is 100 mcg/kg MGD020 + 300 mcg/kg MGD014, Cohort -1 of Part 1B would receive 30 mcg/kg MGD020 (MTD_{1A}/MAD_{1A} -2 dose from Part 1A) + 300 mcg/kg MGD014.

Participants who completed Part 1A may be considered for enrollment in Part 1B, provided they meet all eligibility criteria, did not experience DLT in Part 1A, and do not have detectable ADA against MGD014 and/or MGD020 at the completion of Part 1A.

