b For participants who have been previously exposed to MGD014 or MGD020, obtain screening samples for ADA (MGD014 and MGD020) at least 21 days prior to enrollment to allow for results to be reported before enrollment.

c PK, ADA and cytokine samples may be obtained selectively at additional time points in participants who experience signs and symptoms of IRR or CRS.

Abbreviations: ADA: anti-drug antibody; CRS: cytokine release syndrome; EOI: end of infusion; EOS: end of study; HLA: human leukocyte antigen; IPDA: intact proviral DNA assay; IRR: infusion related reaction; N/A: not applicable; PBMC: peripheral blood mononuclear cell; PD: pharmacodynamic; PK: pharmacokinetic.

Table 11 Pharmacokinetic, Immunogenicity, and Pharmacodynamic Sampling Schedule: Part 2

Study Day	Time Point	Window	PK ^a (Serum)		ADA (Serum)		Cytokines (Serum)	PD: T-cell Binding & Phenotype (Whole Blood)	PD: IPDA & rca- RNA (PBMCs)	HLA Typing (Whole Blood)	PD: QVOA (Leuka- pheresis)	PD: SCA (Plasma)
			MGD020	MGD014	MGD020	MGD014						
-56 to -1	Screening	N/A			X ^b	X ^b					X ^c	
1	Pre-MGD020 infusion	N/A	X	X			X	X	X	X		X
1	EOI MGD020	+ 10 min	X									
1	EOI MGD014	+ 10 min		X								
1	1 h after EOI MGD014	± 5 min	X	X			X	X				
1	4 h after EOI MGD014	± 5 min	X	X			X	X				
2	No specific time	N/A	X	X			X	X				
4	No specific time	N/A	X	X								
8	No specific time	± 1 day	X	X			X	X				
15	Pre-MGD020 infusion	N/A	X	X	X	X	X	X				
15	EOI MGD020	+ 10 min	X									
15	EOI MGD014	+ 10 min		X								
15	4 h after EOI MGD014	± 5 min	X	X			X	X				
29	Pre-MGD020 infusion	N/A	X	X	X	X	X	X				
29	EOI MGD020	+ 10 min	X									
29	EOI MGD014	+ 10 min		X								
29	4 h after EOI MGD014	± 5 min	X	X			X	X				
43	No specific time	± 2 days	X	X					X		X ^c	X
50	No specific time	± 2 days	X	X								
64	No specific time	± 3 days	X	X								
IRR-CRS ^d	No specific time ^d	N/A	X	X	X	X	X					
78/EOS	EOS	± 3 days	X	X	X	X						X

a Obtain pre-infusion PK samples before start of infusion on visit day (dosing day) or day before. When collecting multiple samples, collect PK sample first.

b For participants who have been previously exposed to MGD014 or MGD020, obtain screening samples for ADA (MGD014 and MGD020) at least 21 days prior to enrollment to allow for results to be reported before enrollment.

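### In Part 1A no ADA exclusion reaches people previously given MGD014, so a positive screening ADA result to MGD020 does not bar dosing with MGD020

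*Protocol*

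**What the plan says.** Protocol Section 5.2 contains three criteria that bear on the point.

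- Exclusion 2 bars "History of any HIV-1 vaccine or HIV-1 immunotherapy, except MGD014 or MGD020, within 6 months prior to screening". Prior MGD014 is therefore accepted.
- Exclusion 20 bars "For participants with prior exposure to MGD020, positive ADA to MGD020".
- Exclusion 21 bars "For participants with prior exposure to MGD014, positive ADA to MGD014 (Part 1B or Part 2 only").

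Section 2.3 describes the molecules as "identical in structure except for the sequences of the anti-HIV-1 env arms, which recognize different epitopes of the HIV-1 env". Sections 2.3.1 and 2.3.2 give both an hXR32-derived CD3 arm and a mutated human IgG1 Fc domain. Section 2.3.1.1 states that this is the first study of MGD020 in humans.

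For participants moving from Part 1A to Part 1B, Section 4.1.2 (repeated in SAP Section 3.3) requires that they "do not have detectable ADA against MGD014 and/or MGD020 at the completion of Part 1A". Section 4.1.3 and SAP Section 3.4 have a parallel rule for Part 2.

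In Appendix 2, Table 9 (Part 1A) draws an MGD020 ADA sample at screening and no MGD014 ADA sample. Footnote b to Tables 10 and 11 (Parts 1B and 2) tells sites, for anyone previously exposed to either drug, to "obtain screening samples for ADA (MGD014 and MGD020) at least 21 days prior to enrollment to allow for results to be reported before enrollment". Table 9 has no such footnote.

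**The concern.** Part 1A is meant to describe MGD020 alone: its safety, its PK and the dose at which escalation stops. A participant who arrives with antibody that binds MGD020 can disturb this in either direction. Faster clearance would make a dose level look better tolerated than it is in an antibody-free person. A reaction driven by the antibody could count as a DLT that belongs to the earlier exposure.

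The cohorts are very small, and the Part 1A MTD or MAD fixes the MGD020 doses in Part 1B (Protocol Table 2), so an error would carry forward.

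Confining exclusion 21 to the parts in which MGD014 is given is understandable. That reasoning does not explain why a positive result against MGD020 has no consequence when MGD020 is the drug about to be infused.

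**Working it through.** **1. Apply the criteria as written.** Take a candidate given MGD014 before, never given MGD020, entering a part directly.

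| Screening ADA positive to | Part 1A | Part 1B or Part 2 |
|---|---|---|
| MGD014 only | not excluded (21 does not apply; not sampled) | excluded by 21 |
| both drugs | not excluded | excluded by 21 |
| MGD020 only | not excluded (20 needs prior MGD020) | not excluded (20 needs prior MGD020) |

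Every Part 1A cell is open. In Parts 1B and 2 only the last row is open. Carry-over antibody to the shared arm or Fc would be expected to bind MGD014 as well, which puts it in a row that exclusion 21 catches.

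**2. Cohort sizes (Protocol Sections 4.1.1 to 4.1.3 and 14.1).** The plan's maximum reproduces:

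- Part 1A: 3 × (1+3) + 3 × (3+3) = 30
- Part 1B: 3 × 6 = 18
- Part 2: 6
- Total: 54

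With no DLTs, Part 1A is 3 × 1 + 3 × 3 = 12 people. One participant is 1/1 = 100% of an initial cohort 1 to 3 and 1/3 = 33% of an initial cohort 4 to 6.

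**3. What one such participant could do.** The documents give no effect sizes, so the ranges below are assumptions that show leverage only.

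*PK.* If ADA lowers one participant's AUC by a fraction r, the geometric mean of a cohort of n changes by (1 − r)^(1/n) − 1.

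| r | n = 3 | n = 1 |
|---|---|---|
| 25% | −9% | −25% |
| 50% | −21% | −50% |
| 75% | −37% | −75% |

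*DLTs in a 3+3 cohort.* Let the base DLT risk be 10% and let one of the initial three have risk q.

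- Probability of exactly one DLT (expansion) = q × 0.9² + (1 − q) × 2 × 0.1 × 0.9
- Probability that the dose is declared above the MTD = P(two or more) + P(exactly one) × (1 − 0.9³), where 1 − 0.9³ = 0.271

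| q | Exactly one | Two or more | Declared above MTD |
|---|---|---|---|
| 10% | 0.243 | 0.028 | 0.094 |
| 30% | 0.369 | 0.064 | 0.164 |
| 50% | 0.495 | 0.100 | 0.234 |

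*The opposite direction.* Suppose the true DLT risk is 30% and ADA removes one participant's risk altogether. The chance of no DLT in an initial cohort of three rises from 0.7³ = 0.343 to 0.7² = 0.49. In a cohort of one it rises from 0.70 to 1.

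**4. Whether the analysis compensates.** SAP Section 4.4 uses one safety population for safety, PK, PD and immunogenicity. SAP Section 4.11 makes the assessment of ADA impact on safety and PK optional, and gives no category to baseline-positive participants whose titer does not change. Neither step undoes an escalation decision already taken.

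**5. Sampling against rules.** Table 9 draws the MGD020 sample, but no criterion acts on it for MGD014-exposed people and nothing requires the result before dosing. The roll-over rule also refers to MGD014 ADA at the end of Part 1A, which Table 9 does not sample; the Part 1B screening sample could supply it.

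**The case against.** The strongest opposing case has five parts.

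- **No contradiction.** A reader might infer that the either-drug rule in Sections 4.1.2 and 4.1.3 contradicts exclusions 20 and 21. It does not. It covers people who completed an earlier part of this study and is added to the eligibility criteria, so both can be applied. What stands is a difference in logic: a person given only MGD020 in Part 1A is barred from Part 1B by ADA to MGD014, while a person given only MGD014 is not barred by ADA to MGD020.
- **Parts 1B and 2.** A reader might infer that the gap is equally wide there. Step 1 shows that it is not. Exclusion 21 and footnote b catch antibody that binds MGD014, leaving only a person positive solely in the MGD020 assay, which the carry-over mechanism does not predict.
- **No incidence data.** It is tempting to multiply an assumed ADA rate by the 21 single-dose MGD014 participants in Section 2.3.2.1. The documents support no such count: incidence, persistence and specificity are not given, nor is the number of the 21 who would be candidates. Six of them (1 + 1 + 4) had a single dose of 1 mcg/kg or less. This objection stands in full.
- **The ADA endpoint.** A reader might infer that ADA incidence is distorted. The screening sample identifies baseline positives, and Protocol Section 14.5.2 and SAP Section 4.11 separate them from baseline-negative participants who convert. This endpoint is largely protected.
- **Other safeguards.** Exclusion 16 bars "Participation in another investigational clinical research study within 60 days prior to screening", with exceptions for certain studies. Exclusion 17 bars investigational therapy within 90 days before the first dose, exclusion 8 bars known hypersensitivity, and exclusion 1 leaves room for investigator judgement. Section 4.2 considers safety data beyond the DLT window and adds three participants at a prior level that had only one if the next dose exceeds the MTD. These limit the harm, and the one-participant share describes a single escalation step, not the final MTD. None of them tests for ADA, and judgement cannot act on a result that need not be available before enrollment.

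**Conclusion.** The point holds for Part 1A. As written, an MGD014-exposed person with a positive screening ADA result to MGD020 may receive MGD020 in its first-in-human cohorts, and no criterion acts on that result. This follows from the text and needs no assumption.

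That such antibody would bind MGD020 and alter exposure or tolerability is an inference from the shared CD3 arm and Fc. Frequency, cross-reactivity and effect are unreported, so the size of the risk is unknown, and the PK and DLT figures above show only how far one participant could move a cohort. The residual gap in Parts 1B and 2 is narrow.

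This is a cheap improvement to the eligibility wording. It does not show that the design is unsound.

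**What to change.** Reconcile exclusions 20 and 21 with Sections 4.1.2 and 4.1.3 and with the Appendix 2 sampling tables.

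- Replace the two drug-by-drug exclusions with one criterion: for anyone previously exposed to MGD014 or MGD020, positive ADA to a study drug given in that part is exclusionary. In Part 1A that drug is MGD020. This also closes the MGD020-only row in Parts 1B and 2.
- Attach the results-before-enrollment requirement of footnote b to the Table 9 screening MGD020 ADA sample for previously exposed candidates.

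The sample is already in the schedule, so no new draw is needed, and the maximum of 54 participants is unchanged. The cost is a wait of about three weeks (the 21 days in footnote b, within the 56-day screening window) for previously exposed candidates, and the possible exclusion of a few of them.
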